#### 13.1.1 Determination of Sample Size

A sample of 25 patients will provide 86% power to detect the hypothesized reduction in Ki67 with 5% alpha based on a two-sided, one sample t-test of mean percent change in Ki67 level, based on prior data for Ki67 changes in the tamoxifen only arm of the IMPACT trial. To account for attrition (estimated 20% screen failure/withdrawal rate) and 10% rate of unmatched pre- versus post-treatment biopsy samples, a sample of 35 patients is proposed for this study.

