## 7. STUDY OBJECTIVES

### 7.1 Primary Objective

- To evaluate Ki67 before and after treatment with the mTORC1/2 inhibitor TAK-228 plus the non-steroidal agent tamoxifen in patients with newly diagnosed ER-positive, HER2-negative breast cancer.

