## 13. STATISTICAL AND QUANTITATIVE ANALYSES

### 13.1 Statistical Methods

Based on prior data for Ki67 changes in the tamoxifen only arm of the IMPACT trial, we will assume null and alternative hypotheses of 60% and 80% reduction in Ki67, respectively. Transformations of the geometric mean and 95% CI were employed to obtain mean and standard deviation estimates.

As a measure of safety, toxicity will be monitored during the trial based on a beta-binomial model, assuming a priori that the probability of toxicity  $p$  is distributed beta(0.2, 0.8). Study accrual will be suspended and the safety profile of the TAK-228 and tamoxifen combination will be reviewed by the safety monitoring committee if  $P_r(p > .20 | \text{data}) > 0.85$ . This stopping rule yields the following stopping bounds where the numerator represents the number of events needed to suspend accrual and the denominator represents the number treated at that point in the study: 3/6, 4/8, 5/12, 6/16, 7/20, 8/24. An event is defined as progression within 16 weeks. Scenario 1 of the operating characteristics table (see below) indicates that the probability of stopping the study early for progression is very low when progression is uncommon; that is, the study has only a 4.2% chance of stopping early when the true progression rate is only 10%. The study has a 94.3% chance of stopping if the true progression rate is 40% and on average would take only 7 patients to arrive at that conclusion. The stopping rule assumes monitoring begins after 6 patients have been enrolled on study.

Scenario	True $P_r(\text{toxicity})$	$P_r(\text{stop early})$	Median # Pts (25%, 75%)
1	0.10	0.042	28 (28, 28)
2	0.20	0.317	28 (15, 28)
3	0.30	0.723	14 (6, 28)
4	0.40	0.943	7 (6, 13)
5	0.50	0.995	6 (6, 7)

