#### **13.1.6 Efficacy Analysis**

The single-arm, single-stage, phase II IMPACT clinical trial will be utilized to assess changes in Ki67 levels. Ki67 levels will be log transformed (natural logarithm) to achieve approximately normally distributed data. The difference between the log-transformed values in pre- and post-treatment biopsy samples will be calculated. Based on prior data for Ki67 changes in the tamoxifen arm alone, we will assume null hypothesis and alternative hypotheses of 60% and 80% reduction in Ki67, respectively. Transformations of the geometric mean and 95% CI presented in Dowsett et al. were employed to obtain mean and standard deviation estimates. A sample of 25 patients will provide 86% power to detect the hypothesized reduction in Ki67 with 5% alpha based on a two-sided, one sample t-test of mean percent change in Ki67 level. To account for attrition (estimated 20% screen failure/withdrawal rate) and 10% rate of unmatched pre- versus post-treatment biopsy samples, a sample of 35 patients is proposed in the study.

We assume that the combination will double the pCR rate compared to tamoxifen alone. Assuming a pCR rate of 10% for tamoxifen alone, a one-tailed one sample test for population proportions based on the lower confidence limit of a Wilson's Score interval will achieve 68.6% power at the 0.10 significance level to detect a pCR rate increase due to the addition of TAK-228 to tamoxifen assuming the true pCR rate of the combination is 20%. Assuming a true pCR rate of 20% for the combination, we expect a lower bound for the Wilson Score 90% one-sided confidence interval of 12.4%. The power calculation is based on a simulation of 20,000 replications using the BINOMIAL option of the FREQ procedure of SAS. All statistical analyses will be conducted using SAS 9.4 (SAS Institute Inc., Cary, NC, USA).

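### The only primary Ki67 test is described on two incompatible scales, log difference and mean percent change, and the SD behind the 86% power is not given

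*Combined protocol and SAP*

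**What the plan says.** The primary objective (Section 7.1) is "To evaluate Ki67 before and after treatment with the mTORC1/2 inhibitor TAK-228 plus the non-steroidal agent tamoxifen", and Section 8.1 makes the change in Ki67 the only primary endpoint. Neither section gives a scale.

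Section 13.1.6 then describes the analysis in two ways:

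- **Log scale.** "Ki67 levels will be log transformed (natural logarithm) to achieve approximately normally distributed data", and "The difference between the log-transformed values in pre- and post-treatment biopsy samples will be calculated". The planning values fit this scale: "Transformations of the geometric mean and 95% CI were employed to obtain mean and standard deviation estimates" (Section 13.1, repeated in 13.1.6).
- **Percent scale.** The only test named, in 13.1.1 and again in 13.1.6, is a "two-sided, one sample t-test of mean percent change in Ki67 level".

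For the hypotheses, Section 13.1 says "we will assume null and alternative hypotheses of 60% and 80% reduction in Ki67, respectively", and 13.1.6 repeats this. Neither says whether the reductions are in the geometric or the arithmetic mean. Section 13.1.1 claims 86% power with 25 patients at two-sided 5%. The SD behind that figure is not printed, nor are the geometric mean and confidence interval it came from.

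**The concern.** A t-test on log differences asks whether the geometric mean of the post/pre ratios differs from a reference. A t-test on percent changes asks the same of the arithmetic mean of the individual changes. Ratios are usually right-skewed, and then the arithmetic mean ratio is larger than the geometric one, so the same figure of 60% is a different null on each scale.

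This is the trial's only primary analysis. An analyst who follows the sentence naming the test would run something other than the steps set out just before it. In an open-label single-arm trial the choice could also be made after the data are seen. Without an SD, a reader cannot tell from the 86% which scale was used for planning.

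**Working it through.** **Inputs.** From 13.1.1: n = 25 (24 df), two-sided 5%, power 86%. From 13.1 and 13.1.6: null 60% and alternative 80% reduction, that is, post/pre ratios of 0.40 and 0.20. The SD is not given. Assumption for all simulations: log-normal ratios, 200,000 trials per scenario.

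**1. Can 86% be reproduced?** Not forwards, because there is no SD. Solved backwards with the noncentral t (noncentrality d√25), 86% power needs d = 0.634. Any power that rounds to 86% needs d between 0.629 and 0.639.

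- Log scale: difference ln(0.40/0.20) = ln 2 = 0.693, so SD = 0.693/0.634 = 1.09 (range 1.09 to 1.10).
- Percent scale: difference 20 points, so SD = 20/0.634 = 31.6 points (range 31.3 to 31.8).

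The two implied SDs are so different that printing the planning SD would show which scale was used.

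**2. Geometric reading of 60% and 80% (better supported), log SD s = 1.09.** The arithmetic mean ratio is the geometric ratio × exp(s²/2), and exp(1.0935²/2) = 1.818.

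- Null: 0.40 × 1.818 = 0.727, an arithmetic reduction of 27.3%.
- Alternative: 0.20 × 1.818 = 0.364, an arithmetic reduction of 63.6%.

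A literal percent-change test against 60% therefore has a true mean only 3.6 points beyond its null at the alternative, and far short of it at the null. Simulated results:

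| Test | Power at alternative | False benefit at null |
|---|---|---|
| Log difference against ln(0.40) | 86% | 2.5% |
| Percent change against 60% | 22% | under 0.1% |
| Percent change against 27.3% (re-expressed null) | 84% | 14% |

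At the null, the literal test against 60% also rejects towards less reduction in about 29% of trials. At the alternative, the log test shows benefit and the literal test does not in about 64% of trials. The two were never significant in opposite directions, at the null or at the alternative. Moving the percent-scale null restores power, but false benefit rises well above the nominal 2.5%, because a t-test with n = 25 copes poorly with this skew.

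**3. Sensitivity to the unknown log SD.**

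| Log SD | Log test power | Percent change against 60%: power | Re-expressed null: power | Re-expressed null: false benefit |
|---|---|---|---|---|
| 0.8 | 98.6% | 67% | 96% | 9% |
| 1.0 | 91.4% | 33% | 88% | 12% |
| 1.09 | 86% | 22% | 84% | 14% |
| 1.2 | 79.1% | 14% | 80% | 16% |

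**4. Arithmetic reading (less supported), SD 31.6 points.** At the null the mean ratio is 0.40 and the SD 0.3155. The log SD is √ln(1 + (0.3155/0.40)²) = 0.696, and the geometric ratio is 0.40 × exp(−0.696²/2) = 0.314, a geometric reduction of 68.6%. A log test against ln(0.40) then falsely shows benefit in about 39% of trials. So ln(0.40) should not be adopted without confirming that the 60% is geometric.

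**The case against.** The strongest reply is that 13.1.6 sets out an ordered procedure (log-transform, take differences, plan from a geometric mean and its interval), and that mean percent change is only a loose label for the back-transformed result, since exp(mean log difference) − 1 is a geometric mean percent change. The log steps would serve no evident purpose if raw percent changes were tested. On this view the 22% comes from misreading the plan, and the error would be a conservative miss. The 14% belongs to a null that appears nowhere in the plan, and the 39% to the less likely reading.

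Much of this is fair, and the log scale is the better-supported reading. But the plan never states that reconciliation, writes no null for the log difference, and twice names a different test. Following the named test as written would lose the stated power.

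The dependence on a model also stands. At a log SD of 0.6 the literal test would have about 97% power. At 1.09 the log-normal model implies rising Ki67 in about 20% of patients at the null and 7% at the alternative, which the documents neither support nor refute. A normal approximation would give an implied log SD of 1.14 (0.693/0.608) instead of 1.09. The SD may be recoverable from the cited publication, but a reader of the plan cannot check it. None of this removes the conflict over which test is primary.

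**Conclusion.** The concern holds and must be fixed: the primary test is specified on two scales with different nulls, and its power cannot be verified. Neither the 86% nor n = 25 is shown to be wrong. If the 60% and 80% are geometric and the log SD is about 1.09, reading the test sentence literally takes power from 86% to about 22%. Across log SDs of 0.8 to 1.2 the literal test has 67% down to 14%, against 98.6% down to 79.1% for the log test. These sizes rest on log-normal ratios, 25 evaluable pairs and, for the central case, an SD back-solved from the plan's own power. They are not estimates of the trial's true power.

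**What to change.** In Sections 13.1.1 and 13.1.6, replace the reference to mean percent change with text such as: *two-sided one-sample t-test of the mean of ln(post) − ln(pre) against ln(0.40), reported as the geometric mean percent change with its back-transformed 95% CI*. State that 60% and 80% are geometric-mean reductions. If the 60% was derived as an arithmetic mean, re-derive the log-scale null before fixing ln(0.40). Report the log-scale SD used for planning, and restate the power if that SD does not give 86%.

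Two gaps in the existing log step are best closed in the same edit: how a post-treatment Ki67 of zero is handled, since its log is undefined, and which sample counts as post-treatment, since Section 1.1 has tissue taken both at week 6 and from the surgical specimen.

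The core change costs one sentence in two sections plus a planning SD the statistician already has. The two additions need a short rule each. No new data, patients or procedures are needed.

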#### 13.1.2 Randomization and Stratification

Randomization is not employed for this phase II study.

#### 13.1.3 Populations for Analysis

All patients who received at least 1 dose of the study drugs will be included in a descriptive safety analysis. The safety profiles will be assessed through summaries of AEs, SAEs, AEs leading to treatment

discontinuation, and treatment-related death. The safety analysis will report the frequency of all AEs and laboratory abnormalities, as well as the frequency of dose interruptions, dose reductions, and toxicity-related treatment discontinuation. Toxicity rates will be presented using the worst NCI CTCAE version 4.03 grade per patient.

#### **13.1.4 Procedures for Handling Missing, Unused, and Spurious Data**

Data quality control will be performed on a regular basis by the research coordinator/research nurse to ensure timely, accurate, and complete patient data collection. Queries will be generated and resolved prior to the generation of interim and final summary reports.

#### **13.1.5 Demographic and Baseline Characteristics**

Demographic and baseline characteristics will be summarized for all patients participating in the study using descriptive analysis. Classification of patients as responders versus non-responders will be based on treatment response and changes in associated proliferation markers.

#### **13.1.6 Efficacy Analysis**

The single-arm, single-stage, phase II IMPACT clinical trial will be utilized to assess changes in Ki67 levels. Ki67 levels will be log transformed (natural logarithm) to achieve approximately normally distributed data. The difference between the log-transformed values in pre- and post-treatment biopsy samples will be calculated. Based on prior data for Ki67 changes in the tamoxifen arm alone, we will assume null hypothesis and alternative hypotheses of 60% and 80% reduction in Ki67, respectively. Transformations of the geometric mean and 95% CI presented in Dowsett et al. were employed to obtain mean and standard deviation estimates. A sample of 25 patients will provide 86% power to detect the hypothesized reduction in Ki67 with 5% alpha based on a two-sided, one sample t-test of mean percent change in Ki67 level. To account for attrition (estimated 20% screen failure/withdrawal rate) and 10% rate of unmatched pre- versus post-treatment biopsy samples, a sample of 35 patients is proposed in the study.

We assume that the combination will double the pCR rate compared to tamoxifen alone. Assuming a pCR rate of 10% for tamoxifen alone, a one-tailed one sample test for population proportions based on the lower confidence limit of a Wilson's Score interval will achieve 68.6% power at the 0.10 significance level to detect a pCR rate increase due to the addition of TAK-228 to tamoxifen assuming the true pCR rate of the combination is 20%. Assuming a true pCR rate of 20% for the combination, we expect a lower bound for the Wilson Score 90% one-sided confidence interval of 12.4%. The power calculation is based on a simulation of 20,000 replications using the BINOMIAL option of the FREQ procedure of SAS. All statistical analyses will be conducted using SAS 9.4 (SAS Institute Inc., Cary, NC, USA).

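### The pCR test's 68.6% power goes with an attained one-sided type I error of about 14%, not 0.10; no sample size up to 35 gives both stated figures

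*Combined protocol and SAP*

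**What the plan says.** Section 13.1.6 sets up the pCR comparison from two rates: "Assuming a pCR rate of 10% for tamoxifen alone" and, for the alternative, "assuming the true pCR rate of the combination is 20" per cent. The test is "a one-tailed one sample test for population proportions based on the lower confidence limit of a Wilson's Score interval", and it is said that this "will achieve 68.6% power at the 0.10 significance level to detect a pCR rate increase". The section adds that "we expect a lower bound for the Wilson Score 90% one-sided confidence interval of 12.4" per cent. On method it says: "The power calculation is based on a simulation of 20,000 replications using the BINOMIAL option of the FREQ procedure of SAS".

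No sample size is attached to this test. The only sizes in the section are 25 (evaluable for Ki67) and 35 (enrolled). Section 13.1.1 explains the gap between them: "To account for attrition (estimated 20% screen failure/withdrawal rate", with a further 10% allowed for unmatched biopsies. The operating-characteristics table in section 13.1 runs to a maximum of 28 patients. Section 13.1.3 defines one population only: "All patients who received at least 1 dose of the study drugs will be included in a descriptive safety analysis". No pCR-evaluable population is defined.

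**The concern.** The power was simulated, so it is the actual rejection probability of a discrete rule. The significance level printed beside it carries no qualification, and for a score-type limit on a small binomial sample the nominal level can differ a good deal from the attained one. A reader will naturally take 0.10 as the false-positive rate that goes with 68.6% power.

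If the two figures do not belong to the same rule at the same sample size, the plan overstates how well the test separates 10% from 20%. Because the sample size is not given, the reader cannot check this from the text. Attained alpha also moves sharply with the number evaluable, so an undefined denominator leaves the error rate open until the data are in.

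**Working it through.** **Inputs.** Null rate 0.10, alternative 0.20, one-sided 90% Wilson lower limit (z = 1.2816), 20,000 replications: all from section 13.1.6. Enrolment 35 and attrition 20%: section 13.1.1.

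**Rule.** With p̂ = x/n, the lower limit is

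L(x, n) = [p̂ + z²/(2n) − z·√(p̂(1−p̂)/n + z²/(4n²))] / (1 + z²/n).

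The cut-off r is the smallest x with L > 0.10. Attained alpha is P(X ≥ r) at p = 0.10, and power is P(X ≥ r) at p = 0.20, both exact binomial.

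**Step 1: which n lies behind 68.6%?** The simulation standard error is √(0.686 × 0.314 / 20,000) = 0.0033. The 95% range around the stated power is therefore 68.0% to 69.2%.

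| n | Cut-off | Attained alpha | Power at 20% | Mean lower limit at 20% |
|---|---|---|---|---|
| 25 | 5 | 9.8% | 57.9% | 12.0% |
| 27 | 5 | 12.7% | 65.2% | 12.25% |
| **28** | **5** | **14.2%** | **68.5%** | **12.35%** |
| 29 | 5 | 15.8% | 71.6% | 12.45% |
| 30 | 6 | 7.3% | 57.3% | 12.5% |
| 31 | 6 | 8.3% | 60.7% | 12.6% |
| 32 | 6 | 9.4% | 64.0% | 12.7% |
| 33 | 6 | 10.6% | 67.1% | 12.8% |
| 34 | 6 | 11.9% | 70.0% | 12.9% |
| 35 | 6 | 13.2% | 72.8% | 12.95% |

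Among n = 20 to 35, only n = 28 falls in the range. The nearest others, n = 33 and n = 34, are each more than 4 standard errors away. The 12.4% bound, read as the mean limit, fits n = 28 (and n = 29, whose power does not fit). The arithmetic of the plan points the same way: 35 × 0.8 = 28 after attrition, and 28 × 0.9 = 25.2 once unmatched biopsies are removed, which is the Ki67 figure of 25.

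**Step 2: the rule at n = 28.**
- L(5, 28) = [0.1786 + 0.0293 − 1.2816 × √(0.00524 + 0.00052)] / 1.0587 = 0.1045, above 0.10.
- L(4, 28) = 0.0779, below 0.10. The cut-off is therefore 5.
- Power = 1 − P(X ≤ 4 | 0.20) = 1 − 0.3149 = 0.6851, which reproduces the plan's 68.6%.
- Attained alpha = 1 − P(X ≤ 4 | 0.10) = 1 − 0.8579 = 0.1421.

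**Step 3: can any cut-off at n = 28 give both figures?**
- At 6 or more, alpha is 0.0550 and power 0.4995. No whole-number cut-off lies between 5 and 6.
- A randomised test of size exactly 0.10 would reject at 5 with probability (0.10 − 0.0550)/0.0871 = 0.5166. Its power would be 0.4995 + 0.5166 × 0.1856 = 0.595.

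**Step 4: does the conclusion depend on n = 28?** No. Over n = 20 to 35, whenever attained alpha is 0.10 or less, power is at most 64.0% (n = 32). The first size with power of at least 68.6% and alpha of at most 0.10 is n = 39 (8.9%, 68.8%). That exceeds planned enrolment, and its mean lower limit is 13.2%, not 12.4%.

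**Step 5: varying denominator.** If evaluable n is binomial(35, 0.8) (an assumption), the Wilson rule averages alpha 11.5% and power 63.5%. A rule based on the exact (Clopper-Pearson) limit averages 6.4% and 52.2%. With 5 pCRs, the Wilson rule declares success at n = 29 and not at n = 30.

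**The case against.** The best defence is that nothing has been miscalculated. The power and the expected bound both reproduce at n = 28. A 90% one-sided Wilson limit is a nominal 0.10 test by construction, and the plan nowhere calls 0.10 exact or a ceiling. Score intervals aim at the nominal error on average rather than in the worst case: the mid-p value at 5 of 28 is 0.0986, and the average alpha over varying n is 11.5%, closer to nominal than 14.2%. The 14.2% itself rests on an inferred n. If the 12.4% is read as the limit at an observed 20%, it points to n = 31, where alpha is 8.3%. Finally, pCR is secondary, and no stopping or enrolment decision hangs on it.

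Part of this stands. The excess comes from discreteness, not from a mistake in the power. Keeping a nominal-level rule is legitimate. The Wilson rule does determine the cut-off once n is known, so the cut-off is open only because the denominator is.

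The rest does not rescue the sentence. At n = 31 power is 60.7%, so that size cannot be the source of 68.6%. The mid-p value does not change how often the stated rule rejects under the null. An attained power is printed next to an unqualified level, and simulating the same rule at 10% would have shown about 14%.

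**Conclusion.** The concern holds. The pair of 68.6% power and 0.10 significance is not available at any sample size from 20 to 35. At n = 28, the size that fits the plan's figures, that power comes with an attained one-sided alpha of 14.2%, about 1.4 times the stated level.

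The 14.2% rests on the inference that n = 28. The broader conclusion, that 0.10 is only nominal for a test with this power, does not. Over n = 25 to 35 the Wilson rule's alpha runs from 7.3% to 15.8% and its power from 57.3% to 72.8%.

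This is a misstated operating characteristic of a secondary endpoint in a single-arm trial sized on Ki67. It should be corrected, but it has no bearing on enrolment or on the primary analysis.

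**What to change.** In section 13.1.6, state the planning size for the pCR test (28, if the sponsor confirms it). In section 13.1.3, define the pCR-evaluable population. Before any data are seen, fix the decision rule for whatever evaluable n is realised. Then choose one of two forms.

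**(a) If 0.10 is meant as a ceiling**, use the exact limit:

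> Superiority to 10% is declared if the one-sided 90% Clopper-Pearson lower limit exceeds 10% (5 or more pCRs at n = 25; 6 or more at n = 26 to 32; 7 or more at n = 33 to 35). At n = 28, attained alpha is 5.5% and power at 20% is 50%.

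**(b) If 0.10 is meant as nominal**, keep the present test:

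> Superiority to 10% is declared if the one-sided 90% Wilson lower limit exceeds 10% (nominal 0.10; 5 or more pCRs at n = 25 to 29; 6 or more at n = 30 to 35). At n = 28, attained alpha is 14.2% and power at 20% is 68.5%.

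Option (b) is the smaller change and is enough to make the statement correct. Option (a) trades power for a guaranteed ceiling, which is a choice rather than a correction. Either costs two or three sentences and a less favourable stated power (a) or alpha (b). No extra patients are needed.

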#### **13.1.7 PK/Biomarkers**

Plasma PK of the TAK-228 plus tamoxifen combination will be determined on days 1 and 15. Blood samples for PK analysis will be obtained 1 hour ( $\pm$  15 minutes) before TAK-228 dosing and 1 hour ( $\pm$  5 minutes) after TAK-228 dosing. Blood samples (10 mL per sampling timepoint) will be collected and plasma batched for future analyses. Banked tumor tissue obtained as part of the patient's standard care and collected biopsy tissues will be evaluated for tissue-based biomarkers including ER; Ki67; mitotic index; apoptosis; levels of S6K1, 4EBP-1, EIF4E, EIF4G, and EIF4A; levels of phosphorylated S6K, p53, p63, and p73 levels; and p73 and p63 gene signatures. These biomarkers will be compared to clinical parameters such as tumor response to help define a biomarker signature associated with p63/p73 and/or PI3K/AKT dependence and NFkB in ER-positive breast cancers and to identify new therapeutic options for ER-positive breast cancer patients. Oncotype DX testing will also be performed on biopsy and surgical

tissue samples.

